Subject Population: Male or female subjects, between 18 and 60 years of age, inclusive, with a diagnosis of schizophrenia with persistent negative symptoms of schizophrenia.

Number of Subjects:	Number of Sites:
Approximate number of subjects per treatment group:	Approximately 48 sites in North America and Europe
TAK-831 50 mg QD: 52	
TAK-831 125 mg QD: 52	
TAK-831 500 mg QD: 52	
Placebo QD: 78	
Estimated total: 234 randomized	

Dose Levels:	Route of Administration:
TAK-831 50 mg QD	Oral
TAK-831 125 mg QD	
TAK-831 500 mg QD	
Placebo QD	
Duration of Treatment:	Period of Evaluation:
12 weeks	Approximately 20 weeks from screening visit to final visit (4 weeks of screening, a 14-day single-blind placebo run-in period, 12 weeks of double-blind treatment, and 10 to 14 days of follow-up).

Main Criteria for Inclusion:

- The subject has a current diagnosis of schizophrenia as defined by the MINI 7.0.2 for Psychotic Disorders for the Diagnostic and Statistical Manual of Mental Disorders, Fifth Edition (DSM-5) and the general psychiatric evaluation.
- The subject's initial diagnosis must be ≥ 1 year from screening.
- The subject is male or female and aged 18 to 60 years, inclusive.
- The subject is receiving primary background antipsychotic therapy (other than clozapine) at a total daily dose between 2 mg and 6 mg of risperidone equivalents (as outlined in an Antipsychotic Reference document). Concomitant treatment with a subtherapeutic dose of a second antipsychotic may be permitted with sponsor or designee approval if used to treat specific symptoms such as insomnia, but not if it is used for refractory positive psychosis symptoms.
- The subject is treated with a stable regimen of psychotropic medications with no clinically meaningful change (no increase in dose, ≤25% decrease in dose for tolerability) in the 2 months prior to the screening visit and no dose adjustment is anticipated throughout study participation up to the Day 84/early termination visit.
- The subject has a BNSS total score (12-item, excluding number 4) ≥28; stable single-blind placebo run-in and baseline BNSS total (12-item, excluding number 4) scores (≤20% change from the screening score).
- The subject has no more than moderate-severe (≤5) rating on PANSS positive symptom items P1, P3, P4, P5, P6, or unusual thought content (G9), with a maximum of 2 of these items rated "5"; no more than moderate (≤4) rating on conceptual disorganization (P2).

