The primary endpoint will be analyzed by comparing TAK-831 and placebo over all assessed time points using estimates from a mixed model for repeated measures (MMRM) with baseline value as a covariate; pooled site, visit,

treatment, and categorical age (randomization factor) as fixed factors; and treatment-by-visit and baseline-by-visit interactions. Based on a Missing at Random Assumption, this analysis will be performed using observed case data only. The effect at each time point for each treatment is allowed to vary freely and an unstructured covariance matrix is assumed. If the model does not converge, other covariance structures (unstructured, compound symmetry, 2-Toeplitz, etc) will be considered. Additional analyses to address sensitivity to missing data will be specified in the statistical analysis plan.

Multiplicity will be controlled across dose-arms by first testing the 125 mg QD and 500 mg QD dose-arms in parallel using Holm's method to control the overall type I error at the 0.10 level (one-sided), then testing the 50 mg QD dose-arm at the 0.10 level if at least 1 of other doses is found to be statistically superior to placebo.

Secondary Efficacy Analyses

Other change from baseline endpoints will be analyzed in the same manner as the primary endpoint, but without control for multiple doses. The change from baseline on the CGI-SCH-S at Day 84, and the CGI-SCH-I score at Day 84 will be analyzed using a Cochran-Mantel-Haenszel test. This analysis will be stratified by age and performed using observed cases only.

Interim Analysis

An interim analysis for futility may be performed during the study, allowing for early study termination if the probability of success on the primary endpoint fails to meet a pre-specified criterion. The specifics of this analysis will be included in an interim analysis plan that will be finalized before interim unblinding.

Sample Size Justification:

Assuming that the effect size is at least 0.4 for the 125 mg QD and 500 mg QD doses and that at least 85% of the 234 subjects complete the Day 84 assessment, the study has at least 82% power for at least 1 dose to be statistically-significant at the 0.10 level with correction for multiple doses.

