13.1.3 Efficacy Analysis

13.1.3.1 Analysis of Primary Efficacy Endpoint

The primary endpoint will be analyzed by comparing TAK-831 and placebo over all assessed time points using estimates from a mixed model for repeated measures (MMRM) with baseline value as a covariate; pooled site, visit, treatment, and categorical age (randomization factor) as

fixed factors; and treatment-by-visit and baseline-by-visit interactions. Based on a Missing at Random Assumption, this analysis will be performed using observed case data only. The effect at each time point for each treatment is allowed to vary freely and an unstructured covariance matrix is assumed. If the model does not converge, other covariance structures (unstructured, compound symmetry, 2-Toeplitz, etc) will be considered.

Additional analyses to address sensitivity to missing data will be specified in the SAP.

Multiplicity will be controlled across dose-arms by first testing the 125 mg QD and 500 mg QD dose-arms in parallel using Holm's method to control the overall type I error rate at the 0.10 level (one-sided), then testing the 50 mg QD dose-arm at the 0.10 level if at least 1 of other doses is found to be statistically superior to placebo.

In order to provide additional insight about dose-response, the primary endpoint may be analyzed using a Multiple Comparison Procedure-Modeling (MCP-Mod) approach. Additional details of the MCP-Mod analysis will be specified in the SAP.

Before unblinding the data, the team will assess the degree of impact from COVID-19 on PANSS NSFS data completeness or collection modality. If the impact is deemed minimal, which is defined as less than 5% of the enrolled subjects having remote or missing final assessments due to COVID-19, then the original analysis plan will be followed. If there is more than a minimal impact, then a more thorough blinded review will be performed. After the blinded assessment, if substantial changes to the statistical analyses are needed to address the impact, the SAP will be amended before study unblinding. Minor changes may be documented in the clinical study report.

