13.3 Determination of Sample Size

Assuming that the effect size is at least 0.4 for the 125 mg QD and 500 mg QD doses and that at least 85% of the 234 subjects complete the Day 84 assessment, the study has at least 82% power for at least 1 dose to be statistically-significant at the 0.10 level with correction for multiple doses.

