Permuted block randomization will be used. The randomization will be stratified by age at Screening (<35 and ≥35 years of age). The allocation ratio will be 2:2:2:3 to the 3 TAK-831 arms and placebo arm respectively.

A schematic of the study design is included as Figure 4.a.

Figure 4.a Schematic of Study Design

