7.9 Efficacy Analysis

The analyses and summaries for efficacy will be based on the FAS, unless otherwise noted.

7.9.1 **Primary Efficacy Endpoint(s)**

The primary endpoint is the change from Baseline on the PANSS NSFS at Day 84. The details of PANSS NSFS calculation can be found in Section 7.9.4.

The primary endpoint will be analyzed by comparing TAK-831 and placebo over all assessed time points using estimates from a mixed model for repeated measures (MMRM) with Baseline value as a covariate; pooled site, visit, treatment, and categorical age (randomization factor) as fixed factors; and treatment-by-visit and Baseline-by-visit interactions. Based on a Missing at Random Assumption, this analysis will be performed using observed case data only. The effect at each time point for each treatment is allowed to vary freely and an unstructured covariance matrix is assumed. If the model does not converge, other covariance structures (unstructured, compound symmetry, 2-Toeplitz, etc) will be considered.

Multiplicity will be controlled across dose-arms by first testing the 125 mg QD and 500 mg QD dose-arms in parallel using Holm's method to control the overall type I error rate at the 0.10 level (one-sided), then testing the 50 mg QD dose-arm at the 0.10 level if at least 1 of other doses is found to be statistically superior to placebo.

In order to provide additional insight about dose-response, the primary endpoint may be analyzed using a Multiple Comparison Procedure-Modeling (MCP-Mod) approach (Pinheiro et al, 2014).

For MCP-Mod approach, DoseFinding package in R statistical analysis software will be used. R has been validated by the contract research organization for this study. The following set of models will be fit to detect a dose response: linear, E_{max} , quadratic, and exponential. The stratification factor of age (<35 and \geq 35 years) will be included in the models. Each of the dose-response shapes in these models will be evaluated using optimal contrasts and applying MCP-Mod techniques to preserve the family-wise error rate (FWER) with the overall 1-sided significance level of 0.10. The effective dose(s) will be determined within this framework. The stratification factor of age may be omitted if the dose response for the stratified models cannot be reliably estimated.

The following supplementary analyses will also be conducted for the primary endpoint:

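### The dose-testing rule does not hold the overall type I error at one-sided 0.10: one high-dose success opens two further tests at the full 0.10, and the error rate can reach about 17%

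*SAP*

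**What the plan says.** SAP 7.9.1 sets out two steps for the primary endpoint, the change from baseline in PANSS NSFS at Day 84.

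- **Step 1:** "Multiplicity will be controlled across dose-arms by first testing the 125 mg QD and 500 mg QD dose-arms in parallel using Holm's method", at an overall one-sided 0.10.
- **Step 2:** "then testing the 50 mg QD dose-arm at the 0.10 level if at least 1 of other doses is found to be statistically superior".

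Protocol 13.1.3.1 gives the same rule, and the Protocol 2.0 summary repeats it. Neither document divides alpha between the second Holm test and the 50 mg test, or reduces it for either.

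The design inputs are in Protocol 2.0 and 13.3 and SAP 4.4: 52 subjects on each dose and 78 on placebo ("The allocation ratio will be 2:2:2:3 to the 3 TAK-831 arms and placebo arm respectively"), a standardised effect of at least 0.4 for both high doses, and at least 85% of the 234 subjects completing Day 84. The stated power is at least 82% for at least one dose to be significant.

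**The concern.** Holm on two hypotheses uses all of the 0.10. The smaller p-value is tested at 0.05 and, if that test succeeds, the other high dose is tested at 0.10. No alpha is left for a third hypothesis until both high doses have been rejected. The plan nevertheless opens 50 mg at 0.10 after a single rejection.

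The rule fails when exactly one high dose is effective and the other high dose and 50 mg are not. The true success then opens two tests of true nulls, each at 0.10. A dose-response in which only the top dose works is of this kind. Protocol 6.2.2 expects peak target occupancy near the maximum at 500 mg and less at the lower doses, so the case cannot be set aside.

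What is at stake is a superiority claim for a dose that does nothing. In a trial meant to tell three doses apart, such a claim could carry an ineffective dose forward, at a rate well above the one stated.

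**Working it through.** **Inputs.** Completers: 0.85 × 52 = 44.2 per active arm and 0.85 × 78 = 66.3 on placebo. Effects are in SD units. One-sided critical values: 1.645 for 0.05 and 1.2816 for 0.10.

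**Standard error and correlation.** SE = √(1/44.2 + 1/66.3) = 0.194. Two dose-placebo statistics share the placebo mean, so their correlation is (1/78)/(1/78 + 1/52) = 52/130 = 0.40.

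**Reproducing the plan's power.** The expected z at effect 0.4 is 0.4/0.194 = 2.06. Power for one dose at 0.05 is Φ(2.06 − 1.645) = 0.661. Power for at least one of the two high doses is 1 − Φ₂(1.645 − 2.06, 1.645 − 2.06; 0.40) = 0.828. This agrees with the stated figure of at least 82%. Splitting a two-sided 0.10 (0.025 per test) would give 0.723, and no correction (0.10 per test) would give 0.913. The plan's power therefore rests on Holm at one-sided 0.10 with the arm sizes above.

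**Limit in the failing case.** Let 500 mg be so effective that it is always rejected, with 125 mg and 50 mg null. Each null dose is then tested at 0.10:

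P(at least one false claim) = 1 − Φ₂(1.2816, 1.2816; 0.40) = 0.10 + 0.10 − 0.0267 = 0.173.

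Independent tests would give 1 − 0.9² = 0.19, and the Bonferroni bound is 0.20.

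**Finite effects.** The full rule was evaluated by numerical integration over the shared placebo mean. Simulation with 2,000,000 replicates per scenario agrees to within about 0.1 percentage point. At effect 0.4 for 500 mg, 125 mg is falsely rejected with probability 0.093 and 50 mg with 0.089. The overlap is 0.026, so the total is 0.093 + 0.089 − 0.026 = 0.156.

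| True state | P(at least one false dose claim), plan | 50 mg tested only after both high doses |
|---|---|---|
| All doses null | 9.1% | 9.1% |
| Only 500 mg works, effect 0.4 | 15.6% | 9.3% |
| Only 500 mg works, effect 0.5 | 16.7% | 9.8% |
| Only 500 mg works, effect 0.6 | 17.2% | 9.9% |
| Only 500 mg works, limit | 17.3% | 10.0% |
| 125 and 500 mg both 0.4, 50 mg null | 9.7% | 8.9% |
| Only 50 mg works, effect 0.4 | 9.1% | 9.1% |

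By symmetry, the rates are the same if 125 mg is the only effective dose.

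**The case against.** The arithmetic is not in dispute. The case on the other side has four parts.

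- **The excess appears in one configuration only.** If 125 mg has even a small effect (0.1 or 0.2) beside 500 mg at 0.4, with 50 mg null, the error is 9.0% to 9.2%. The planning assumption is an effect of at least 0.4 for both high doses, and Protocol 6.2.2 predicts pharmacodynamic effects at all three doses. This stands as a limit on scope: the failing case is possible, not the expected one. Strong control must nevertheless cover it, and a pharmacodynamic effect does not guarantee efficacy.
- **The 0.10 may refer only to the Holm pair, for which it holds.** The phrase about overall error does follow the mention of Holm. But the sentence opens with control across dose arms and goes on to include 50 mg. If only the pair is meant, the text should say so.
- **This is phase 2, and each null dose taken alone is still claimed at most 10% of the time.** Both are true, and a wholly inactive drug yields any claim only about 9% of the time. But the rule produces dose-specific claims and states an overall rate for them. That rate is wrong under a partial null.
- **Other analyses inform dose choice.** MCP-Mod is optional, and the exposure-response work is exploratory. They soften the practical harm without repairing the pairwise rule.

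**Conclusion.** The concern holds. As written, the rule gives weak control (9.1% under the global null) but not the control across dose arms that both documents state. When exactly one high dose is effective and the other two doses are not, the probability of at least one false dose claim is 15.6% at the planning effect of 0.4. It rises to a limit of 17.3%, against a stated 10%. These figures assume normal test statistics, the planned 52/52/52/78 allocation, 85% completers in every arm, and a correlation of 0.40 from the shared placebo. The limit depends only on the critical value and that correlation, not on the effect size or the amount of dropout. The 82% power statement concerns Step 1 and is unaffected.

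**What to change.** Amend SAP 7.9.1, Protocol 13.1.3.1 and the Protocol 2.0 summary before unblinding, in one of three ways.

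1. **Test 50 mg at one-sided 0.10 only if both 125 mg and 500 mg are rejected by Holm.** Error in the failing case becomes 9.3% at effect 0.4 and 10.0% in the limit. Power for at least one high dose stays at 82.8%. If all three doses have effect 0.4, power to claim 50 mg falls from about 69% to 55%.
2. **If 50 mg should stay reachable after one success, test 125 mg and 500 mg at 0.05 each without Holm's second step.** Then test 50 mg at 0.05 if exactly one is rejected and at 0.10 if both are. Error is 8.6% to 9.1% in the failing case for effects of 0.4 and above, and at most 10% overall. Power for at least one high dose is again unchanged. Power for 50 mg is 64%, but power for each high dose falls from 73% to 66%.
3. **Keep the rule and withdraw the claim.** State that the 0.10 applies to the 125/500 mg pair only and that the error across all three doses is not controlled at that level.

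The choice between the first two depends on how much the sponsor values a 50 mg claim against a claim for each high dose. All three options are wording changes, with no effect on sample size, data collection or the stated power.

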6.0 DETERMINATION OF SAMPLE SIZE

Assuming that the effect size is at least 0.4 for the as 125 mg QD and 500 mg QD doses and that at least 85% of the 234 subjects complete the Day 84 assessment, the study has at least 82% power for at least 1 dose to be statistically significant at the 0.10 level with correction for multiple doses.

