- 1) A method for missing value imputation based on pattern mixture models (PMM) using standard SAS STAT procedures. It is assumed that after discontinuation from the study, subjects receiving a TAK-831 dose will exhibit the same future evolution of the disease as subjects on the placebo treatment. The missing PANSS NSFS scores in the TAK-831 dose arm will be imputed using placebo-based pattern mixture models. This method uses sequential regression and multiple imputation methodology to impute missing values for visits after a subject's discontinuation from the study in the placebo arm. Then based on the available data from placebo subjects, the missing values for mactive treatment arm will be imputed using pattern mixture models until missing values at all visits are imputed.
- 2) The primary endpoint also be analyzed using analysis of covariance (ANCOVA), with pooled center, stratification factor, and treatment as fixed factors, and PANSS NSFS Baseline score as a covariate. ANCOVA based on the multiply-imputed data will be performed.

As a supportive analysis, the primary endpoint will be analyzed using MMRM in the same manner as described in section 7.9.1, but based on the PPS.

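### The optional MCP-Mod analysis names age as its only covariate; taking the primary MMRM's Day 84 means and covariance as its input would be a free, minor gain in precision

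*SAP*

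**What the plan says.** Protocol 13.1.3.1 makes MCP-Mod optional and leaves the method to the SAP: "Additional details of the MCP-Mod analysis will be specified in the SAP".

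SAP 7.9.1 keeps it optional: "In order to provide additional insight about dose-response, the primary endpoint may be analyzed using a Multiple Comparison Procedure-Modeling (MCP-Mod) approach". It cites a methods paper, names the R package and lists four candidate shapes (linear, Emax, quadratic, exponential). It sets a one-sided family-wise level of 0.10. On covariates it says that the age factor "will be included in the models. Each of the dose-response shapes in these models will be evaluated using optimal contrasts", and later: "The stratification factor of age may be omitted if the dose response for the stratified models cannot be reliably estimated". It attaches a purpose to the result: "The effective dose(s) will be determined within this framework".

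The MCP-Mod paragraph says nothing about baseline NSFS, pooled site or subjects without a Day 84 value. It does not say whether the input is each subject's Day 84 change or a set of model estimates.

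The other models for this endpoint in SAP 7.9.1 are fuller. The primary MMRM is specified "with Baseline value as a covariate; pooled site, visit, treatment, and categorical age (randomization factor) as fixed factors", plus interactions of treatment and of baseline with visit. The supplementary ANCOVA uses "pooled center, stratification factor, and treatment as fixed factors, and PANSS NSFS Baseline score as a covariate".

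**The concern.** One endpoint is modelled three ways in one section. Two of the models adjust for baseline. The third, on its most natural reading, does not. The clause that lets age be dropped fits direct entry of age into the dose-response models better than it fits the use of MMRM estimates, where age has already been adjusted for.

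Baseline NSFS is collected on everyone and usually explains part of the Day 84 variation. Leaving it out cannot sharpen the contrasts or the fitted curves, apart from a trivial degree-of-freedom saving, and may blur them. At stake is the precision of the framework in which the SAP says effective doses will be determined. Two programmers could also follow the paragraph and produce different results.

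**Working it through.** **1. The plan's own power figure.** SAP section 6.0 assumes an effect size of 0.4 for 125 mg and 500 mg and that "at least 85% of the 234 subjects complete the Day 84 assessment", and states at least 82% power for at least one dose.

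- Completers: 0.85 x 78 = 66.3 on placebo and 0.85 x 52 = 44.2 per TAK-831 arm.
- SE of a difference in SD units: sqrt(1/66.3 + 1/44.2) = 0.194, and 0.4/0.194 = 2.06.
- The first Holm step is one-sided 0.05, so power per dose is Phi(2.06 - 1.645) = 66.1%.
- The shared placebo arm gives the two tests a correlation of 44.2/110.5 = 0.4. Power for at least one dose is then 82.8%.

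The stated figure reproduces. It belongs to the Holm-tested comparisons, and MCP-Mod does not enter it.

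**2. Variance with and without baseline.** Set the Day 84 SD to 1, the baseline SD to k and their within-arm correlation to r. Neither document gives k or r, so both are assumed.

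- Unadjusted Day 84 change has variance 1 + k^2 - 2rk.
- Change adjusted for baseline has residual variance 1 - r^2.
- Proportional inflation from omitting baseline: (1 + k^2 - 2rk)/(1 - r^2) - 1 = (k - r)^2/(1 - r^2).

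This is a square over a positive number, so it is never negative. It is zero when r = k, that is, when the baseline slope r/k equals 1.

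| Variance inflation | r = 0.4 | r = 0.5 | r = 0.6 | r = 0.7 | r = 0.8 |
|---|---|---|---|---|---|
| k = 1.0 | 42.9% | 33.3% | 25.0% | 17.6% | 11.1% |
| k = 0.9 | 29.8% | 21.3% | 14.1% | 7.8% | 2.8% |
| k = 0.8 | 19.0% | 12.0% | 6.3% | 2.0% | 0.0% |
| k = 0.7 | 10.7% | 5.3% | 1.6% | 0.0% | 2.8% |

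The largest entry means a standard error sqrt(1.429) = 1.195 times as large, or 19.5% wider. Six of the 20 cells are below 5%, seven lie between 5% and 15%, and seven are above 15%.

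**3. Cost of adjusting.** About 0.85 x 234 = 199 subjects complete. With four arm means, one age term and one baseline slope, the extra coefficient costs about 1/(199 - 6) = 0.5% in variance.

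The table treats the MMRM as its baseline adjustment alone. No gain is claimed from using earlier visits, from pooled site or from handling dropouts.

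**The case against.** The strongest reply is that silence is not exclusion. The SAP says age will be in the models; it does not say only age. Nothing in the paragraph rules out MMRM estimates as input, and it cites a methods paper that I have not relied on. If MMRM input was intended, the gain is zero and the sentence only records the intent. This stands, and it is why the point is an improvement to the specification.

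The analysis is also optional, carries no share of the Holm alpha and gates no test. That stands too.

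The upper end of the range comes from one corner of an assumed grid. That is correct, so the result should be read as a range with zero inside it.

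Several stronger readings are tempting, and the documents do not support them:

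- **The MCP-Mod paragraph is an error, or contradicts the primary analysis.** It is a less complete model for a different, supportive purpose.
- **The primary result or the 82% power is weakened.** Step 1 of the working shows that neither depends on MCP-Mod.
- **Without the fix, MCP-Mod would often disagree with the Holm tests.** The two procedures can differ by design. Any rate of disagreement would need shape parameters and a 50 mg effect that the documents do not give, and disagreement is not a measure of lost precision.
- **Dropout would bias MCP-Mod.** The paragraph has no rule for missing Day 84 values, but the size of any effect depends on dropout patterns that the documents do not describe.
- **Omitting pooled site matters.** SAP 7.2.5 pools sites into two groups, European and non-European, and no effect of leaving that factor out has been shown.

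**Conclusion.** The point holds as a minor, free improvement. SAP 7.9.1 names age alone for MCP-Mod, allows it to be dropped without a numerical criterion, and states no link to a baseline-adjusted MMRM of the same endpoint. On the age-only reading, the variance behind the contrast tests and fitted curves is 0% to 43% larger than it need be, for r of 0.4 to 0.8 and k of 0.7 to 1.0. Adjustment costs about 0.5%. Both r and k are assumptions, and a k above 1 would raise the figure. The inflation is zero if the baseline slope is 1 or if MMRM input was already meant. Confidence is medium, because the intended input is not stated.

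**What to change.** In the MCP-Mod paragraph of SAP 7.9.1, remove both age sentences: the one that puts age in the models and the one that lets it be omitted. Removing only the second would leave a requirement that cannot be met when the input is four means. Put in their place:

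> If MCP-Mod is performed, the contrast tests and the model fits will use as input the four Day 84 LS means and their covariance matrix from the primary MMRM, which already adjusts for baseline NSFS, pooled site and age.

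Missing Day 84 values are then handled under the same missing-at-random assumption as in the primary analysis. If the reference to stratified models was meant to allow age-specific dose-response curves, the SAP should say so separately, because these LS means average over age.

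The cost is one sentence in place of two, made before unblinding. It uses output that the primary analysis already produces and changes no confirmatory test. It does not supply the candidate-shape parameters or a target effect for the effective dose, which are separate gaps.
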